5.3 Data Analysis General Considerations

5.3.1 Pooling of Centers

Subjects from all centers will be pooled for all analyses.

5.3.2 Adjustments for Covariates

The randomization stratification by age group will be reflected in models for the analysis of the primary and secondary PD endpoints by incorporating age group as a fixed effect.

5.3.3 Multiple Comparisons/Multiplicity

No multiplicity adjustments will be made for this is a Phase 1 safety study.

5.3.4 Examination of Subgroups

Separate analyses will be performed for the 2 age groups (≥ 45 and < 65 years and ≥ 65 to 90 years) for the primary and secondary PD endpoints in addition to the analyses in which age group is treated as a covariate. Separate analyses also will be performed for subjects with moderate OSA ($15 \leq \text{AHI} < 30$) and severe OSA ($\text{AHI} \geq 30$) and for subjects with moderate COPD (GOLD 2 Classification) and severe COPD (GOLD 3 Classification) if there are sufficient numbers of subjects in the subgroups.

5.3.5 Handling of Missing Data, Dropouts, and Outliers

In general, missing values due to subject discontinuation, missed or unusable assessments will not be imputed.

Incomplete/Missing data will not be imputed, unless otherwise specified; i.e., all missing values will remain as missing in all statistical analyses and listings, unless otherwise specified.

No formal statistical analyses will be performed to detect and/or remedy the presence of statistical outliers.

5.3.6 Other Considerations

The OSA and COPD cohorts will be analyzed separately. If one of the cohorts completes earlier than the other, the database may be locked for that cohort and the data analyzed before the database is locked for the other cohort.

Individual subject data in the database will be presented in data listings.

For the analyses of the primary and secondary endpoints the estimands will be the difference between lemborexant and placebo for the difference from baseline. The PD analysis set will be used for these analyses and since the endpoints are safety endpoints, the assignment of treatment group will be the treatment actually received. Any missing values will be considered to be missing at random. In a previous lemborexant study in subjects with OSA, missing values were due to dropout for administrative reasons.

5.4 Efficacy Analyses

No efficacy data will be collected in this study.

5.5 Pharmacokinetic, Pharmacodynamic, Pharmacogenomic, and Other Biomarker Analyses

The Safety Analysis Set will be used for individual lemborexant and M4, M9 and M10 plasma concentration listings. The PK Analysis Set will be used for summaries of lemborexant and M4, M9 and M10 plasma concentrations. Since only 1 blood sample for PK determination will be obtained on each study day, no PK parameters will be calculated.

5.5.2 Pharmacokinetic/Pharmacodynamic Analyses

Pharmacokinetic/Pharmacodynamic (Exposure-Response) Analyses

The exposure-response (E-R) relationship between plasma concentrations of lemborexant after PSG, and selected PD parameters including but not limited to the respiratory safety variables (including AHI, mean SpO₂ during TST, ODI, absolute number of desaturations, and percentage of TST in which SpO₂ is <90%, <85%, and <80%) will be explored graphically. Any emergent relationship may be followed using population model-based analysis. The potential effect of covariates (eg, age) on the E-R relationship may be tested. The PK Analysis Set will be used for these assessments.

5.5.3 Pharmacogenomic/Pharmacogenetic and Other Biomarker Analyses

Not applicable.

5.6 Safety Analyses

All safety analyses will be performed on the Safety Analysis Set. Safety data, presented by treatment group, will be summarized on an “as treated” basis using descriptive statistics (eg, n, mean, standard deviation, median, minimum, maximum for continuous variables; n [%] for categorical variables). Safety variables include treatment-emergent adverse events (TEAEs), clinical laboratory parameters, vital signs, 12-lead ECG results, and the C-SSRS. Study Day 1 for all safety analyses will be defined as the date of the first dose of study drug.

The incidence of AEs, out-of normal-range markedly abnormal laboratory variables, out-of-range vital signs, and suicidality variables (C-SSRS) will be summarized by treatment for OSA and COPD cohorts using descriptive statistics.

5.6.1 Extent of Exposure

The extent of exposure (mean daily dose, cumulative dose [calculated as the sum of the daily doses], and duration of exposure) to each treatment will be summarized descriptively by treatment and cohort, and a listing will also be provided.

5.6.2 Adverse Events

The AE verbatim descriptions (investigator terms from the CRF) will be classified into standardized medical terminology using the Medical Dictionary for Regulatory Activities (MedDRA). Adverse events will be coded to the MedDRA (Version 19.0 or higher) lower level term (LLT) closest to the verbatim term. The linked MedDRA preferred term (PT) and primary system organ class (SOC) will also be captured in the database.

A treatment-emergent adverse event (TEAE) is defined as an AE that emerged during treatment, having been absent at pretreatment (Baseline) or

- Reemerged during treatment, having been present at pretreatment (Baseline) but stopped before treatment, or
- Worsened in severity during treatment relative to the pretreatment state, when the AE was continuous.

Only those AEs that are treatment emergent will be included in summary tables. All AEs, treatment emergent or otherwise, will be presented in subject data listings.

The TEAEs will be summarized by treatment group separately for each cohort. The incidence of TEAEs will be reported as the number (percentage) of subjects with TEAEs by SOC and PT. A subject will be counted only once within a SOC and PT, even if the subject experienced more than 1 TEAE within a specific SOC and PT. The number (percentage) of subjects with TEAEs will also be summarized by maximum severity (mild, moderate, or severe). The number (percentage) of subjects with treatment-related TEAEs will be summarized by SOC and PT. Treatment-related TEAEs include those events considered by the investigator to be related to study treatment. The number (percentage) of subjects with treatment-related TEAEs will also be summarized by maximum severity (mild, moderate, or severe) (*or by highest CTCAE grade*).

A TEAE in Treatment Period 1 is counted up to predosing of Treatment Period 2 a TEAE in Treatment Period 2 is counted up to the final study visit.

Separate listings will be provided for subjects with deaths, SAEs, and AEs leading to discontinuation.

5.6.3 Laboratory Values

Laboratory results will be summarized using Système International (SI) units, as appropriate. For all quantitative parameters listed in protocol Section 9.5.1.5 Safety Assessments (Laboratory Measurements), the actual value and the change from baseline to each postbaseline

visit and to the end of treatment (defined as the last on-treatment value) will be summarized by cohort using descriptive statistics (eg, mean, SD, median, minimum, maximum for continuous variables, and number and percentage for categorical variables) for the laboratory parameters and changes from baseline.

Qualitative parameters listed in protocol Section 9.5.1.5 will be summarized using frequencies (number and percentage of subjects), and changes from baseline to each postbaseline visit and to end of treatment will be reported using shift tables. Percentages will be based on the number of subjects with both nonmissing baseline and relevant postbaseline results.

Abnormal laboratory values will be identified as those outside (above or below) the normal range. Reference (normal) ranges for laboratory parameters will be included in the clinical study report for this study. Laboratory test results will be assigned a low-normal-high (LNH) classification according to whether the value was below (L), within (N), or above (H) the laboratory parameter's reference range. Within-cohort comparisons will be based on 3 by 3 tables (shift tables) that, for a particular laboratory test, compare the Study Baseline LNH classification to the LNH classification at end of study/early termination, by treatment group.

Clinical laboratory results postbaseline will be evaluated for markedly abnormal values. A laboratory test will be considered markedly abnormal if the result worsens to meet Eisai grading criteria for laboratory values limit of Grade 2 or higher. If the Grade 2 limit is missing, the Grade 1 limit will be considered. [Appendix 13.1](#) presents the Eisai grading criteria for laboratory values that were used to identify subjects with markedly abnormal laboratory values. For the incidence of markedly abnormal laboratory values, each subject may be counted once in the laboratory parameter value high and in the laboratory parameter low categories as applicable.

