#### 9.5.1.4.7 OTHER SAFETY ASSESSMENTS

##### **Columbia-Suicide Severity Rating Scale**

The C-SSRS assesses an individual's degree of suicidality, including both suicidal ideation and suicidal behavior. An assessment of suicidality using the C-SSRS will be performed at Screening, Baseline, at the Follow-up Visit, and as designated in the Schedule of Procedures/Assessments ([Table 4](#)).

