**Table 5 Summary of Blood Sample Volumes (OSA and COPD Cohorts)**

	Sample Volume per Collection (mL)	Number of Collection Time Points	Total Volume Collected (mL)
Clinical laboratory tests	12	Screening: 1 Baseline 1: 1 Follow-up: 1	$12 \times 3 = 36$
PK blood sampling	4	Treatment Period 1: 3 Treatment Period 2: 3	$4 \times 6 = 24$
Biomarker blood sampling	6	Baseline 1: 1 Baseline 2: 1 Treatment Period 1: 1 Treatment Period 2: 1	$6 \times 4 = 24$
Total			84

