5.2.2 Subject Disposition

Reasons for screening failure will be summarized.

The number and percentage of subjects who completed the study will be summarized by treatment group and by sequence, and the number who discontinued prematurely will be summarized by reason for discontinuation by treatment group and by sequence.

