5.6.4 Vital Signs

Descriptive summary statistics for vital sign parameters (diastolic and systolic blood pressure, pulse, and respiration rate) will be evaluated by treatment at predose and at postdose for Day 1 and Day 8. In addition, change from predose to each postdose time will be summarized by treatment. Baseline will be the pre-dose value in each treatment period. Each cohort will be analyzed separately.

Clinically notable ranges will be summarized by treatment and time point and will be defined as follows:

Table 1 Vital Sign Criteria

Variable	Criterion value ^a	Change relative to baseline ^a	Clinically notable range
Heart rate	>120 bpm	Increase of ≥ 15 bpm	H
	<50 bpm	Decrease of ≥ 15 bpm	L
Systolic BP	>180 mmHg	Increase of ≥ 20 mmHg	H
	<90 mmHg	Decrease of ≥ 20 mmHg	L
Diastolic BP	>105 mmHg	Increase of ≥ 15 mmHg	H
	<50 mmHg	Decrease of ≥ 15 mmHg	L

BP = blood pressure, bpm = beats per minute, H = high, L = low.

a. Clinically notable means that a value must meet the criterion value and must attain the specified magnitude of change relative to baseline.

Vital sign values will be listed on an individual basis by cohort, treatment and subject. Abnormal vital sign values will be identified on the listings as those above (H) or below (L) a clinically notable range.

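### SAP 5.6 and 5.6.3 plan laboratory and C-SSRS summaries by treatment, but a completer's only scheduled post-baseline result comes after both treatments

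*SAP*

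**What the plan says.** **By-treatment summaries.** The opening paragraph of SAP 5.6 presents safety data by treatment group, as treated, and lists laboratory parameters, ECG and the C-SSRS among the safety variables. Its next paragraph says that "markedly abnormal laboratory variables, out-of-range vital signs, and suicidality variables (C-SSRS) will be summarized by treatment". SAP 5.6.3 adds shift tables that "compare the Study Baseline LNH classification to the LNH classification at end of study/early termination, by treatment group". The quantitative laboratory sentence in 5.6.3 is already by cohort, but it includes a change from baseline "to the end of treatment (defined as the last on-treatment value) will be summarized by cohort". The sentence on qualitative parameters also refers to end of treatment.

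**Sampling.** The laboratory row of Protocol Table 5 reads "Screening: 1 Baseline 1: 1 Follow-up: 1". The biomarker row of the same table reads "Baseline 1: 1 Baseline 2: 1 Treatment Period 1: 1 Treatment Period 2: 1". Protocol 9.5.1.4.7 has the C-SSRS "performed at Screening, Baseline, at the Follow-up Visit, and as designated in the Schedule of Procedures/Assessments".

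**Neighbouring rules.** For vital signs, SAP 5.6.4 says "Baseline will be the pre-dose value in each treatment period". SAP 5.6.5 summarises ECG at Screening, Baseline and Follow-up with no split by treatment. SAP 5.6.2 and 5.2.5 give rules for assigning adverse events and concomitant medication to a period. No such rule is given for laboratory or C-SSRS results.

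**The concern.** In a crossover, a summary by treatment needs at least one result per subject that belongs to each treatment. For laboratory tests and the C-SSRS, the schedule provides none in a completer. The planned columns would still carry the labels lemborexant and placebo, and a secondary objective (SAP 3.1.2) is safety and tolerability against placebo. Similar columns could be read as reassurance when they say almost nothing about treatment. Because the text gives no attribution rule, the choice would also be left to programming.

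**Working it through.** **1. Count the scheduled results.** Table 5 gives three laboratory draws. Its volumes reproduce: 12 × 3 = 36 mL for laboratory tests, 4 × 6 = 24 mL for PK and 6 × 4 = 24 mL for biomarkers. The sum is 36 + 24 + 24 = 84 mL, the printed total, so no further laboratory blood is budgeted. Two of the three draws (Screening and Baseline 1) precede dosing, which leaves 3 − 2 = 1.

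Table 4 is partly broken in the text available, but by column position it agrees. Laboratory marks fall at Visit 1, Baseline 1, end of study and the discretionary Unscheduled column. Nothing is marked at Baseline 2 or at the end of either period. The C-SSRS row has three marks, the last aligned with discharge from study, so one C-SSRS assessment follows first dose.

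**2. Place that result in time.** Nominal days from Table 4: last Period 1 dose Day 8, last Period 2 dose Day 30, end of study Day 59.

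| Sequence | Last lemborexant dose | Interval to end of study | Lemborexant nights before the result | Placebo nights before the result |
|---|---|---|---|---|
| A, C (placebo first) | Day 30 | 59 − 30 = 29 days | 8 | 8 |
| B, D (lemborexant first) | Day 8 | 59 − 8 = 51 days | 8 | 8 |

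If end of study is taken as 28 days after the final dose (SAP 3.2), the intervals are 28 and 50 days. Either way, a completer has no scheduled on-treatment laboratory value.

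**3. Try the ways to fill the columns.** The SAP states neither of the first two rules below; they are assumptions made to test the text. Take 30 completers per cohort and exact 1:1 allocation.

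- *Assign the result to the last treatment received.* The lemborexant column is 15 subjects from A or C, and the placebo column is 15 from B or D. Every subject in both columns has had 8 lemborexant doses. The columns are different people who differ in sequence and in time since lemborexant (29 against 51 days). Chance or baseline imbalance can also separate them.
- *Count the result under both treatments.* Each column holds the same 30 values, and the difference is 0.
- *Read treatment group as sequence.* SAP 5.2.2 uses the terms as alternatives: "The number and percentage of subjects who completed the study will be summarized by treatment group and by sequence".

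None of these gives a comparison of lemborexant with placebo.

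**4. Subjects who do not complete.** Under Table 4 footnote c, early terminators have an early-termination visit and then an end-of-study visit 28 days later. A subject who stops in Period 2 may therefore have two results. Both follow exposure to both treatments if at least one Period 2 dose was taken. Only a subject who stops before Period 2 dosing has a result that belongs to one treatment.

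**The case against.** The strongest reply is that little is at stake. In moving from protocol to SAP, the quantitative laboratory summary went from visit and treatment group to cohort, and the shift comparison went from within-treatment to within-cohort. The paragraph on marked abnormality in 5.6.3 has no treatment split of its own. What remains is one phrase in the shift-table sentence and the general wording of 5.6. The tables are descriptive and individual data are listed. SAP 9 and 11 place programming rules and table shells in separate documents, where an attribution rule could sit. All of this stands, and it limits the severity. It does not help the SAP text: step 3 shows that neither attribution rule would make a completer's Day 59 result informative about one treatment.

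A second reply is that Protocol 9.1.2 has Period 2 follow the procedures of Period 1. The same section refers routine safety assessments to Table 4, which marks no laboratory test or C-SSRS at Baseline 2 or at either period's end.

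A reader might infer three stronger things that the documents do not support:

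- *Everyone dosed in both periods has exactly one post-baseline result.* That is exact for completers only. A Period 2 stopper may have two, and the early-termination sample may fall close to the last dose.
- *Only a long-lasting drug effect could make the columns differ.* Under a last-treatment rule they hold different people, so chance can too.
- *By-treatment safety reporting fails as a whole.* Adverse events have a period rule and vital signs a baseline in each period. Neither is affected, and nor are the respiratory endpoints.

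**Conclusion.** Wrong as written, and minor. For completers, the by-treatment laboratory shift tables in SAP 5.6.3 and the by-treatment marked-abnormality and C-SSRS summaries in SAP 5.6 cannot support a comparison of lemborexant with placebo. Per cohort, the 30 planned completers each contribute one scheduled post-baseline result and none that belongs to a single treatment. The end-of-treatment laboratory summary has no scheduled value behind it in these subjects.

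This rests on the nominal days in Table 4 and on Table 5 being the full laboratory schedule; unscheduled tests are possible but discretionary. The 15 and 15 split assumes exact 1:1 allocation. The point concerns the SAP text, because the shells and programming specifications were not seen. No hypothesis test or decision rule depends on these tables.

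**What to change.** Change SAP wording only:

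1. In 5.6, including its opening paragraph, limit by-treatment presentation to adverse events and vital signs. State that laboratory results (including markedly abnormal values), C-SSRS and ECG are summarised overall within each cohort, consistent with 5.6.5.
2. In the 5.6.3 shift-table sentence, replace the split by treatment group with a summary overall within each cohort. Keep both end of study and early termination as the comparison point. Remove end of treatment from the quantitative and the qualitative sentences. If a sequence split is shown, label it as sequence.
3. In listings of early-termination and unscheduled results, show sequence, period and the treatments received before the sample. Treat only results obtained before Period 2 dosing as attributable to one treatment.
4. State that scheduled laboratory and C-SSRS results from subjects dosed in both periods do not support a comparison of lemborexant with placebo.
5. Record the departure from Protocol 9.7.1.8 and 9.7.1.8.3 in SAP section 7, which now reports no changes.

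The cost is a few edited sentences and relabelled table shells, with no new sampling and no protocol amendment. The downside is that the nominal by-treatment columns for these data are lost.

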#### 9.7.1.8.3 LABORATORY VALUES

Laboratory results will be summarized using Système International (SI) units, as appropriate. For all quantitative parameters listed in [Section 9.5.1.4.3](#), the actual value and the change from baseline to each postbaseline visit and to the end of treatment (defined as the last on-treatment value) will be summarized by visit and treatment group using descriptive statistics. Qualitative parameters listed in [Section 9.5.1.4.3](#) will be summarized using frequencies (number and percentage of subjects), and changes from baseline to each postbaseline visit and to end of treatment will be reported using shift tables. Percentages will be based on the number of subjects with both nonmissing baseline and relevant postbaseline results.

Laboratory test results will be assigned a low/normal/high (LNH) classification according to whether the value was below (L), within (N), or above (H) the laboratory parameter's reference range. Within-treatment comparisons for each laboratory parameter will be based on 3-by-3 tables (shift tables) that compare the baseline LNH classification to the LNH classification at each postbaseline visit and at the end of treatment. Similar shift tables will also compare the baseline LNH classification to the LNH classification for the highest and lowest value during the treatment period.

[Appendix 1](#) (Sponsor's Grading for Laboratory Values) presents the criteria that will be used to identify subjects with treatment-emergent markedly abnormal laboratory values (TEMAV). Except for phosphate, a TEMA V is defined as a postbaseline value with an increase from baseline to a grade of 2 or higher. For phosphate, a TEMA V was defined as a postbaseline value with an increase from baseline to a grade of 3 or higher. When displaying the incidence of TEMA Vs, each subject may be counted once in the laboratory parameter high and in the laboratory parameter low categories, as applicable.

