Bilirubin (hyperbilirubinemia)	>ULN – 1.5×ULN if baseline was normal; 1.0 – 1.5×baseline if baseline was abnormal	>1.5 – 3.0×ULN if baseline was normal; 1.5 – 3.0×baseline if baseline was abnormal	>3.0 – 10.0×ULN if baseline was normal; 3.0 – 10.0×baseline if baseline was abnormal	>10.0×ULN if baseline was normal; >10.0×baseline if baseline was abnormal
Calcium, serum-low (hypocalcemia)	<LLN – 8.0 mg/dL <LLN – 2.0 mmol/L Ionized calcium <LLN - 1.0 mmol/L	<8.0 – 7.0 mg/dL <2.0 – 1.75 mmol/L Ionized calcium <1.0 – 0.9 mmol/L; symptomatic	<7.0 – 6.0 mg/dL <1.75 – 1.5 mmol/L Ionized calcium <0.9 – 0.8 mmol/L; hospitalization indicated	<6.0 mg/dL <1.5 mmol/L Ionized calcium <0.8 mmol/L; life- threatening consequences

Sponsor's Grading for Laboratory Values

	Grade 1	Grade 2	Grade 3	Grade 4
Calcium, serum-high (hypercalcemia)	>ULN – 11.5 mg/dL >ULN – 2.9 mmol/L Ionized calcium >ULN - 1.5 mmol/L	>11.5 – 12.5 mg/dL >2.9 – 3.1 mmol/L Ionized calcium >1.5 - 1.6 mmol/L; symptomatic	>12.5 – 13.5 mg/dL >3.1 – 3.4 mmol/L Ionized calcium >1.6 - 1.8 mmol/L; hospitalization indicated	>13.5 mg/dL >3.4 mmol/L Ionized calcium >1.8 mmol/L; life-threatening consequences
Cholesterol, serum-high (hypercholesterolemia)	>ULN – 300 mg/dL >ULN – 7.75 mmol/L	>300 – 400 mg/dL >7.75 – 10.34 mmol/L	>400 – 500 mg/dL >10.34 – 12.92 mmol/L	>500 mg/dL >12.92 mmol/L
Creatinine	>ULN – 1.5×ULN	>1.5 - 3.0×baseline; >1.5 – 3.0×ULN	>3.0×baseline; >3.0 – 6.0×ULN	>6.0×ULN
GGT (γ -glutamyl transpeptidase)	>ULN – 2.5×ULN if baseline was normal; 2.0 - 2.5 x baseline if baseline was abnormal	>2.5 – 5.0×ULN if baseline was normal; >2.5 - 5.0 x baseline if baseline was abnormal	>5.0 – 20.0×ULN if baseline was normal; >5.0 - 20.0 x baseline if baseline was abnormal	>20.0×ULN if baseline was normal; >20.0 x baseline if baseline was abnormal
Glucose, serum-high (hyperglycemia)	Abnormal glucose above baseline with no medical intervention	Change in daily management from baseline for a diabetic; oral antidiabetic agent initiated; workup for diabetes	Insulin therapy initiated; hospitalization indicated	life-threatening consequences; urgent intervention indicated
Glucose, serum-low (hypoglycemia)	<LLN – 55 mg/dL <LLN – 3.0 mmol/L	<55 – 40 mg/dL <3.0 – 2.2 mmol/L	<40 – 30 mg/dL <2.2 – 1.7 mmol/L	<30 mg/dL <1.7 mmol/L life-threatening consequences; seizures

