Phosphate, serum-low (hypophosphatemia)	Laboratory finding only and intervention not indicated	Oral replacement therapy indicated	Severe or medically significant but not immediately life-threatening; hospitalization or prolongation of existing hospitalization indicated	life-threatening consequences
Potassium, serum-high (hyperkalemia)	>ULN – 5.5 mmol/L	>5.5 – 6.0 mmol/L	>6.0 – 7.0 mmol/L hospitalization indicated	>7.0 mmol/L life-threatening consequences
Potassium, serum-low (hypokalemia)	<LLN – 3.0 mmol/L	<LLN – 3.0 mmol/L; symptomatic; intervention indicated	<3.0 – 2.5 mmol/L hospitalization indicated	<2.5 mmol/L life-threatening consequences
Sodium, serum-high (hypernatremia)	>ULN – 150 mmol/L	>150 – 155 mmol/L; intervention initiated	>155 – 160 mmol/L hospitalization indicated	>160 mmol/L life-threatening consequences
Sodium, serum-low (hyponatremia)	<LLN – 130 mmol/L	125-129 mmol/L and asymptomatic	<125 – 129 mmol/L symptomatic; 120-124 mmol/L regardless of symptoms	<120 mmol/L life-threatening consequences

Sponsor's Grading for Laboratory Values

	Grade 1	Grade 2	Grade 3	Grade 4
Triglyceride, serum-high (hypertriglyceridemia)	150 – 300 mg/dL 1.71 – 3.42 mmol/L	>300 – 500 mg/dL >3.42 – 5.7 mmol/L	>500 – 1000 mg/dL >5.7 – 11.4 mmol/L	>1000 mg/dL >11.4 mmol/L life-threatening consequences
Uric acid, serum-high (hyperuricemia)	>ULN without physiologic consequences	N/A	>ULN with physiologic consequences	life-threatening consequences

ALT = alanine aminotransferase (serum glutamic pyruvic transaminase), AST = aspartate aminotransferase (serum glutamic oxaloacetic transaminase), N/A = not applicable, LLN = lower limit of normal, ULN = upper limit of normal, WBC = white blood cell.

Based on Common Terminology Criteria for Adverse events (CTCAE) Version 5.0. Published: January 5, 2018.

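### SAP 5.6.3 changes the protocol's definition of a markedly abnormal laboratory value without declaring it: uric acid and phosphate are certainly affected, high glucose only on one reading

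*SAP*

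**What the plan says.** Protocol 9.7.1.8.3 defines a treatment-emergent markedly abnormal value in two parts. For every parameter except phosphate it "is defined as a postbaseline value with an increase from baseline to a grade of 2 or higher". For phosphate it "was defined as a postbaseline value with an increase from baseline to a grade of 3 or higher". There is no provision for a grade that has no entry.

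SAP 5.6.3 has one threshold for all parameters: a value counts once it has worsened to Grade 2 or above. It does not mention phosphate. It then adds: "If the Grade 2 limit is missing, the Grade 1 limit will be considered".

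SAP 13.1 states that its grading table comes from protocol Appendix 1. SAP 7, the place for changes to the planned analyses, is marked not applicable.

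**The concern.** Two rules applied to one grading table can give two different incidences from the same data, and nothing tells the reader of the report that the definition has moved. The fallback pulls the threshold down to a level that the table itself describes as minor. For uric acid that level is ">ULN without physiologic consequences".

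At stake is the meaning of a label in a safety table, in a study run to meet a postmarketing safety requirement (protocol 7.3). A reader who takes the protocol's definition to be in force would over-read the uric acid and phosphate rows.

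**Working it through.** The plan gives no figure on this point to reproduce, so the check sets the two rules against the table row by row.

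**Step 1: where can the fallback act?** The table has 24 rows.
- Grade 2 marked not applicable: 1 row (uric acid).
- Grade 2 filled with a treatment action and no numeric limit: 2 rows (high glucose, low phosphate).
- Grade 2 with a numeric limit: 24 − 1 − 2 = 21 rows.

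The fallback therefore acts on uric acid, and possibly on two further rows.

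**Step 2: lowest grade that counts, if newly reached after baseline.**

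| Parameter | Protocol 9.7.1.8.3 | SAP, Grade 2 entry taken as present | SAP, limit taken to mean a numeric limit |
|---|---|---|---|
| Uric acid, high | Grade 3 (Grade 2 does not exist) | Grade 1 | Grade 1 |
| Phosphate, low | Grade 3 | Grade 2 | Grade 1 |
| Glucose, high | Grade 2 | Grade 2 | Grade 1 |

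- Uric acid differs from the protocol on either reading.
- Phosphate also differs on either reading. Dropping the exception alone lowers the threshold by one grade, to the level at which oral replacement is indicated. Reaching Grade 1, "Laboratory finding only and intervention not indicated", needs the numeric reading as well.
- High glucose differs only on the numeric reading. Its Grade 1 is then "Abnormal glucose above baseline with no medical intervention".

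The numeric reading is plausible, because a laboratory result cannot show that treatment was started or a work-up ordered. It is not compelling: Grade 1 for high glucose and low phosphate has no number either.

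**Step 3: what does not count.** The SAP requires the result to worsen to the grade. A subject whose uric acid was already above ULN without consequences at baseline, and stays so, is not flagged.

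**Step 4: size for uric acid, the certain Grade 1 case.** The documents give no rate of newly raised uric acid, so the rate p is an assumption. With n = 30 completers per cohort (protocol 9.1), the expected number flagged is 30p, and the chance of at least one is 1 − (1 − p)^30.

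| Assumed p | Expected flagged of 30 | Chance of at least one |
|---|---|---|
| 0.025 | 0.75 | 53% |
| 0.05 | 1.5 | 79% |
| 0.10 | 3.0 | 96% |
| 0.20 | 6.0 | >99% |

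Under the protocol rule none of these counts unless there are physiologic consequences (Grade 3).

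**Step 5: which samples feed the table.** Protocol Table 5 schedules clinical laboratory tests at Screening, Baseline 1 and Follow-up. A completer therefore has one scheduled post-baseline sample, about 28 days after the last dose and after both treatments.

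**The case against.** A reader might infer that ordinary glucose values would be reported as markedly abnormal, since protocol 9.4.8.1 sets no food rule. The documents do not support that as a certainty. The Grade 2 cell for high glucose is filled, so on a literal reading the fallback never reaches it. The timing of the follow-up draw relative to meals is not stated, and there is no rate from which to build a count. The same caution applies to Grade 1 phosphate, and to any claim that every raised uric acid counts: only new elevations do.

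It can also be said that the SAP rule is a choice rather than an error. Protocol 9.7.1 leaves further analytical detail to the SAP. The protocol has its own gap for uric acid, where the only level it can count depends on physiologic consequences that a laboratory value cannot show. A fallback fills that gap in the cautious direction. This stands in part: the documents show a different and undeclared rule, and do not establish that the SAP threshold is wrong. It does not excuse the silence, because replacing a stated threshold and dropping a stated exception goes beyond added detail.

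The strongest point is that little depends on it. For completers the single scheduled post-baseline sample is taken off drug after both periods, so it cannot separate lemborexant from placebo under either rule. The table is descriptive, and the shift tables and listings show the same results. All of this stands, and it keeps the point minor.

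**Conclusion.** The mismatch is real, checkable from the text and undeclared. It is certain for uric acid, where a new elevation without consequences counts only under the SAP, and for phosphate, where the stated threshold falls from Grade 3 to Grade 2. Whether the phosphate change alters any count depends on how treatment-based grades are recorded, which neither document says. For high glucose and Grade 1 phosphate, over-flagging is conditional on reading a limit as a numeric limit.

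The only size offered is for uric acid: 1.5 to 3 of 30 per cohort if 5% to 10% newly exceed ULN, resting wholly on that assumed rate. The effect stops at the descriptive marked-abnormality table; the primary AHI and SpO2 analyses are unaffected. This is a minor correction, worth making because it is cheap.

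**What to change.** In SAP 5.6.3:

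- Restore the protocol definition: an increase from baseline to Grade 2 or higher, and to Grade 3 or higher for phosphate.
- Delete the Grade 1 fallback. If it is intended, restrict it to named parameters and declare it in SAP 7, together with any intended change for phosphate.
- State that parameters whose Grade 2 cannot be derived from the laboratory value alone are reported in the low/normal/high shift tables and listings. These are high glucose, low phosphate, uric acid and low potassium. Low potassium belongs here because its Grade 2 repeats the Grade 1 range and adds symptoms or intervention, so a program that sees only values cannot separate the two grades.
- If a treatment-based grade is to be used for any of these, name the data source. Without one, these parameters might never be flagged.

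The cost is a few sentences and one derivation. The downside is fewer flags for these analytes, all of which stay visible in the shift tables and listings.
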